#### TEDDY Participants $\geq$ 15 years of age

Islet autoantibody (IA) positive TEDDY study (COMIRB 04-0361) participants ages 15 and over who have completed the TEDDY protocol will be eligible for the DAISY prospective follow-up. They will be offered autoantibody, HbA1c and random glucose testing every 3-6 months to avoid acute onset of diabetes. Families will receive home glucose monitoring education and will be provided with a glucometer to test blood sugars as recommended. Also a continuous glucose monitor (CGM) or OGTT may be offered for close monitoring of blood glucose levels.

## **2. Consent Procedures:**

Study participants in the sibling/offspring cohort are recruited by telephone/mail or by their physician and asked to come into a study clinic. If the child is younger than 9 months (age of the initial clinic visit) and eligible for telephone interviews, the consent process is completed over the phone and the parents are asked to mail back a copy of the signed consent form prior to the first scheduled telephone interview. These clinics are located on the UC Denver AMC campus at the Barbara Davis Center. Upon arrival, the study participant is given the consent form to read. This is a one-step informed consent to follow-up and genetic testing. The study coordinator or the research nurse goes over the consent form with the study participant sentence by sentence. The research nurse invites questions from the study participant's parent or legal guardian and answers these

questions. The research nurse reads the consent form to the subject's parent or legal guardian when there is a question about the literacy level of the parent or legal guardian. Once the study participant's parent or legal guardian signs the consent form, they are given a copy of the signed consent form, and the data collection begins.

Enrollment of study participants in the general population cohort is in two steps. Consent process for screening is carried out in person by one of the DAISY recruiters at St. Joseph Hospital. The consent to follow-up is identical to that for the sibling/offspring cohort and is completed at the time of the first clinic visit or preceding telephone interview.

Enrolled subjects who develop T1D related autoantibodies or with an HbA1c of >5.7, will be asked to participate in the Continuous Glucose Monitoring (CGM) portion of the DAISY study. The parent or legal guardian will complete a separate consent, entitled "Subject consent for Continuous Glucose Monitoring". We will enroll negative controls into the CGM portion of the study.

DAISY family members and TEDDY siblings who are IA positive and wish to be monitored for progression to T1D will complete a separate consent, DAISY Subject Consent for Family Members, in person with the research nurse, in the same manner as described above, at the next DAISY participant follow up clinic visit.

Training for obtaining written consent: The research clinic staff will undergo training in standard procedures in how to obtain informed consent. [name] and the Research Nurse, [name], have attended the mandatory COMIRB training for investigators. In addition, [name] and [name] are responsible for training the Professional Research Assistants in obtaining the consent, and discussing with them the importance of fully informing subjects of the nature of the study and of complying with COMIRB and OPRR regulations. The clinic staff practices reading the consent form verbatim, in full and role-play in answering questions regarding the consent form and the study. A script has been developed for responding to questions. Any questions that the clinical staff cannot answer are referred to the principal investigator ([name]). Training is completed in approximately 2 hours. The principal investigator and/or research nurse intermittently monitor the consent process in person to assure that protocols and regulations are adhered to.

[figure not shown]
### **3. Treatment, intervention or observation**

This is an observational study. No treatment or intervention will be administered. The prospective follow-up protocol is summarized in the figure and further described below.

Siblings/offspring older than 8 months of age are invited to study clinic for a baseline blood draw and clinic data collection immediately after enrollment. They are seen at the clinic at ages 9, 15, 24 months and annually thereafter. If a child is found to be positive for any of the islet autoantibodies, he/she is placed on an accelerated protocol where the child is seen at the DAISY clinic every 3-6 months to track the natural history of these autoantibodies. Those relatives who meet the entry criteria for the TrialNet Study are followed by TrialNet with intravenous glucose tolerance tests as well as ICA and IAA measurements. As a part of a study ancillary to TrailNet, we continue to follow these children using the regular DAISY protocol.

General population newborns are followed-up only if they meet specific study criteria (see below). The results of newborn HLA screening and an interpretation are mailed to the parents. In addition, parents of moderate and high-risk infants are telephoned to provide genetic risk counseling. To date, all high risk and a sample of moderate and low risk children have been invited to participate in follow-up to determine the age- and genotype-specific incidence of autoimmunity, evaluate its candidate environmental causes as well as promoters of progression from IA to T1D. Eligible children are enrolled after a separate informed consent is signed. When an eligible child's parents decline participation, they are asked to allow telephone contact and medical records review every year, for the purpose of determining the incidence of T1D.

**Figure 1**

Information concerning dietary, infectious and other exposures is collected prospectively over the telephone when the child is 3, 6, 9, 12 and 15 months old (Fig.1). Blood, and urine, are obtained for measurements of exposure and islet autoantibodies. Weight and height are recorded during clinic visits at the ages of 9, 15, 24

months, and yearly thereafter. Body composition (weight and kilograms of body fat) will be measured at every DAISY visit on subjects coming for study visits at the Barbara Davis center or those who are seen at our off site clinic locations using the TANITA® DC-430U Dual Frequency Total Body Composition Analyzer. Blood amount drawn is 15 cc in children whose weight is <10 kg and never exceeds 3 cc/kg in those over 10 kg. If a child is found to be positive for any of the islet autoantibodies, he/she is placed on an accelerated protocol where the child is seen at the DAISY clinic every 3-6 months to track the natural history of these autoantibodies.

DAISY family members and TEDDY siblings are only monitored if previously IA positive, per enrollment criteria above. Approximately 10 cc of blood from these individuals will be collected at the time of the DAISY or TEDDY participants' follow-up clinic visits and tested for plasma glucose level, hemoglobin A1c and IA. No other exposure data will be collected.

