newborn screening programs. This study is likely to exert a sustained, powerful influence on diabetes research by using prospectively defined immuno-genetic phenotypes to advance both personalized medicine and public health approaches to screening and early interventions.

**APPROACH:** We will follow the already established cohort of youth at high risk of T1D and other autoimmune diseases (current n=1149, median age 17.2 y, IQR 13.5-20.2 y) to estimate the overall burden of pre-clinical and clinical T1D, celiac, thyroid, adrenal, rheumatic and parietal autoimmune disease in Colorado by age 25. This will inform future screening and prevention programs. We will further explore the apparent heterogeneity of IA and its implications for adult-onset diabetes.

**Study Population:** Since 1994, DAISY has studied two large cohorts of high-risk children: A) 1,424 general population newborns with high-risk HLA-DR,DQ genotypes; and B) 1,123 non-diabetic relatives of patients with T1D. Cohort to date: 222 persistent IA and 94 progressed to T1D, 5 died, 3 disenrolled due to medical conditions, 265 lost to follow-up; 2180 participants are being tracked and 1149 complete study visits.

General Population High-risk Children During 1993-2004, 31,881 newborns from the general population of Denver, Colorado were screened for HLA-DR,DQ genotypes carrying susceptibility to T1D. 90% of all children born at the St. Joseph's Hospital have participated, representing closely the ethnic breakdown of the Denver Metropolitan Area and including children classified by their mothers as non-Hispanic white (56%), Hispanic (30%), African American (7%), Asian American (2%) or biracial/other (5%). Throughout this application, "DR4" denotes DR4,DQB1\*0302. All children with DR3/4, DR3/3 and DR4/4 and a sample of those with DR4/x or DR3/x were invited to participate in follow-up at ages 9, 15, and 24 months and yearly thereafter; 1,424 completed at least one visit.

Non-diabetic Relatives Non-diabetic offspring and siblings of patients with T1D were invited to participate through the BDC clinics and regardless of their HLA genotype; 1,123 enrolled, at median age 1.4 y and are followed identically to the general population cohort.

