### **Duration of the Study**

Each subject will participate in the study until the index child develops T1D, reaches the age of 40 years- or until funding is no longer available. At age 20, if the subject has developed IA, the study will continue to follow them and monitor IA status, as these individuals will continue to be at an increased risk for T1D.

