#### Family Members

Parents and siblings of the General Population cohort and sibling/offspring cohort are generally studied only once since they are not eligible for prospective follow-up. However, parents or ineligible siblings who are IA positive are offered autoantibody, HbA1c and random glucose testing every 3-6 months to avoid acute onset of diabetes. Families will receive home glucose monitoring education and will be provided with a glucometer to test blood sugars as recommended. The family member may be offered a continuous glucose monitor (CGM) for close monitoring of blood glucose levels if they have an HbA1c >5.7. The CGM data collected will not be used in research analysis. Ages of participants range from 12 months to 65 years.

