#### TEDDY Siblings

Islet autoantibody (IA) positive TEDDY siblings whose parents have consented to the parent/sibling DNA protocol with the TEDDY study are not eligible for the DAISY prospective follow-up. However, these TEDDY siblings are offered autoantibody, HbA1c and random glucose testing every 3-6 months to avoid acute onset of diabetes. Families will receive home glucose monitoring education and will be provided with a glucometer to test blood sugars as recommended. The sibling may be offered a continuous glucose monitor (CGM) for close monitoring of blood glucose levels if they have an HbA1c >5.7. The CGM data collected will not be used in research analysis. Ages of participants range from 12 months to 65 years.

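### IA-positive DAISY family members are offered laboratory testing at 3-6 month intervals, but their blood is drawn at participant visits that are annual unless the participant is antibody-positive, and the end-of-participation rule does not say how it applies to them

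*Protocol*

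**What the plan says.** All references are to the Protocol.

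- **Testing offered to DAISY relatives** (IV.C.1, Family Members): parents, and siblings outside prospective follow-up, if they have IA, "are offered autoantibody, HbA1c and random glucose testing every 3-6 months to avoid acute onset of diabetes".
- **Testing offered to TEDDY siblings** (IV.C.1, TEDDY Siblings): "these TEDDY siblings are offered autoantibody, HbA1c and random glucose testing every 3-6 months to avoid acute onset of diabetes".
- **Home monitoring**: both of these sections also give the families training in home glucose measurement and a glucometer, with CGM possible if HbA1c exceeds 5.7.
- **When their blood is drawn** (IV.C.3, text following Figure 1): "Approximately 10 cc of blood from these individuals will be collected at the time of the DAISY or TEDDY participants' follow-up clinic visits".
- **Participant visit schedule**: for the sibling/offspring cohort (IV.C.3), "They are seen at the clinic at ages 9, 15, 24 months and annually thereafter". For the general population cohort (Specific Aim 1, Approach, General Population High-risk Children), "follow-up at ages 9, 15, and 24 months and yearly thereafter". If a child tests positive for any islet autoantibody, "he/she is placed on an accelerated protocol where the child is seen at the DAISY clinic every 3-6 months".
- **End of participation** (IV.B, Duration of the Study): "Each subject will participate in the study until the index child develops T1D, reaches the age of 40 years". Lack of funds also ends it. The next sentence keeps subjects with IA in follow-up beyond age 20. Relatives and TEDDY siblings are not mentioned.
- **Eligible ages of relatives and TEDDY siblings** (IV.B follow-up criteria; repeated in IV.C.1): 12 months to 65 years.

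**The concern.** For these relatives the laboratory testing has one stated purpose: to avoid an acute onset of diabetes. IV.C.3 says no other exposure data are collected on them. The interval and the draw occasion therefore need to fit together, and for one identifiable group they do not. A test due every 3-6 months cannot be delivered at a visit that takes place once a year.

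A second gap concerns how long the monitoring lasts. The only duration rule is worded around the index child and gives an age limit well below the upper age at which relatives are eligible. Clinic staff could not tell from the text whether an IA-positive parent or sibling stays under monitoring once the index child leaves follow-up.

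What is at stake is the safety monitoring of people already known to have IA.

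**Working it through.** There is no plan figure to reproduce. The check is interval arithmetic and a comparison of the sections.

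**1. Draws offered and draws scheduled, DAISY family members**

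- Offered (IV.C.1): 12 / 6 = 2 to 12 / 3 = 4 tests per year.
- Participant antibody-negative and older than 24 months (IV.C.3; Specific Aim 1): 12 / 12 = 1 visit per year, hence about 1 draw per year if draws follow those visits.
- Shortfall: 2 - 1 = 1 to 4 - 1 = 3 tests per year. The interval is 12 / 6 = 2 to 12 / 3 = 4 times as long as offered.
- Participant younger than 24 months: the visits at 9, 15 and 24 months are 15 - 9 = 6 and 24 - 15 = 9 months apart. The first gap is just within the offer; the second is outside it.
- Participant antibody-positive: visits every 3-6 months, so the two schedules agree.

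The conflict therefore arises where the relative is IA-positive and the DAISY participant is not.

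**2. TEDDY siblings**

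Their draws are tied to TEDDY participants' visits. The Protocol states an interval (3-6 months) only for IA-positive TEDDY participants aged 15 or over who have moved into DAISY follow-up. It gives none for participants still in TEDDY, so no gap can be computed.

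**3. End of monitoring**

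The Duration of the Study section can be read in three ways for a relative:

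| Reading of the rule | Consequence for an IA-positive relative |
|---|---|
| The family's DAISY child | Monitoring ends on another person's diagnosis or age |
| Each subject's own status | Ages above 40 and up to 65, a span of 65 - 40 = 25 years, are eligible but already past the limit |
| Enrolled cohort children only | No end rule is given for relatives, apart from what their own sections imply |

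The sentence about continuing after age 20 does not settle the matter. It does not mention relatives and does not say that it overrides the T1D or age-40 limits.

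**The case against.** Several points against this have force.

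- **The testing is offered, not promised, and the draw sentence does not say that blood is taken only at participant visits.** It could be a convenience rule: share a visit when there is one. That is a fair reading, but it is the only draw occasion the Protocol gives these people, and no separate visit for relatives is described. IV.C.2 likewise has relatives who wish to be monitored sign consent at the DAISY participant's next follow-up visit. An offer at 3-6 months still needs an occasion on which it can be met.
- **A reader might infer that relatives definitely lose monitoring when the index child develops T1D.** The text does not support that. The index child is not defined in that section, the rule may be meant for cohort children only, and an age-40 limit sits badly with eligibility to 65. The rule is ambiguous for relatives; it is not shown to be a stop.
- **A reader might infer an annual schedule for TEDDY siblings too.** The TEDDY visit interval is not in the document, so this cannot be said.
- **A reader might infer that surveillance as a whole would lapse.** It would not. Home glucose monitoring is provided, and CGM may be. These soften the effect of sparser draws but do not supply the HbA1c and autoantibody tests that the offer includes.
- **A reader might size the problem by the 222 of 2,547 participants with persistent IA (222 / 2,547 = 8.7%) or the 94 T1D cases.** Neither counts affected relatives. The first is cumulative over everyone enrolled, while the accelerated schedule is triggered by any positive autoantibody. The second counts participants, not families with an IA-positive relative.
- **The scientific consequence is nil.** This stands: these relatives are outside prospective follow-up, and their CGM data are excluded from research analysis.

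**Conclusion.** The inconsistency is real for IA-positive DAISY family members. Where the participant is antibody-negative and past 24 months, draws tied to that participant's visits come about once a year against the 2 to 4 offered. This assumes that the draw sentence sets the schedule and that no separate visit is arranged. Where the participant is antibody-positive there is no conflict. For TEDDY siblings only the dependence on TEDDY visits is established. The end-of-participation rule is unclear for both groups and does not fit their eligible age range on at least one natural reading.

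The number of relatives affected is not given and could be small. No endpoint, estimate or power figure is touched. The point merits correction because, followed as written, the draw sentence works against the stated purpose of the testing, and the correction is cheap.

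**What to change.** - Reconcile IV.C.1 (Family Members; TEDDY Siblings) with IV.C.3 (visit schedule; draw sentence after Figure 1), so that the testing interval and the occasion of the blood draw agree for IA-positive relatives, including when the participant is on annual visits. For TEDDY siblings, state what visit interval the draws depend on.
- Reconcile IV.B Duration of the Study with the follow-up criteria for family members and TEDDY siblings and with IV.C.1. Say whether the duration rule covers IA-positive relatives and, in either case, whether and when their monitoring ends.

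Which interval and which end rule apply is for the investigator to decide.

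The cost is a few sentences of protocol wording and a check that the separate family-member consent form agrees; that form is not available here. If the 3-6 month offer is kept, no new test is added, though some relatives would need to attend separately from the participant.

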**D. Description, Risks and Justification of Procedures and Data Collection Tools:**

Measurement of islet autoantibodies: Blood samples obtained by venipuncture or a finger stick will be used. We are currently using radioassays for insulin, GAD65, and ICA512 (IA-2) autoantibodies, IAA, GAA, and ICA512AA respectively. IAA are measured in a standard radioimmunoassay incorporating competition with unlabeled insulin and precipitation with polyethylene glycol and in a new microassay. The former requires 600 µl of serum (150 µl duplicates with and without unlabeled insulin). The inter-assay coefficient of variation is 10.3% at low positive levels. In the most recent proficiency testing this assay gave 100% sensitivity and specificity. The microassay, based on protein A/G precipitation, requires 5 µl of serum and appears to be more specific than the large volume assay. GAA are measured in triplicate using a modification of the radioassay with in vitro transcribed and translated human GAD65 and precipitation with protein A-sepharose. The results are expressed as an index:  $GAA \text{ index} = \frac{\text{sample cpm} - \text{negative control cpm}}{\text{positive control cpm} - \text{negative control cpm}}$ . The inter-assay coefficient of variation is 10.7% (n=24). In the most recent Immunology of Diabetes Society Workshop (IDS1995) the assay gave 82% sensitivity and 99% specificity using sera from new onset diabetic patients aged less than 30 years. The ICA512 (IA-2) autoantibodies are measured in a system similar to the GAA assay with the recombinant human ICA512 protein transcribed and translated in vitro with S labelling. The most recent modification of the assay utilizes clone consisting of aminoacids 256 to 979 of human

ICA512. The inter-assay coefficient of variation is 9.6% (n=12). In IDS1995 the assay gave 73% sensitivity and 100% specificity. Over 90% newly diagnosed T1D patients and ICA positive relatives followed to diabetes are positive for either GAD65 or ICA512 using the combined assay. The GAA and ICA512AA are measured in a combined assay using H-labelled GAD65 and S-labelled ICA512 autoantigens and Packard Top beta-counter with protein A sepharose and 96 well filtration.

**Quality control** All samples with GAA or ICA512AA levels exceeding the 99th percentile of the distributions in 198 unrelated non-diabetic persons ages 0.4 - 67.5 years (i.e., GAA >0.032 and ICA512AA>0.16, respectively) and a random 10% of the remaining samples are blindly retested for quality assurance. The IAA testing were repeated if the levels are above 79 nU/ml, rather than above the 99th percentile of non-diabetic distribution (42 nU/ml) because of the large serum required relative to that obtained in these young children. With development of IAA microassay, all positive samples (index >0.01) are re-tested using blinded duplicates.

Primary endpoint for these analyses will be islet autoimmunity (IA) defined as presence of at least one autoantibody (IAA, GAA, ICA512AA), measured according to the protocols described in Specific Aim 1. All such children identified in the sibling/offspring cohort and in the newborn cohort are eligible. The two cohorts will not be combined for analyses. Persistent autoimmunity is defined as presence of at least one autoantibody on at least two separate blood tests. T1D, defined according to the WHO criteria is a secondary endpoint. Hemoglobin A1c and random blood glucose are measured with each blood sample in children positive for any islet autoantibody and the results are reviewed by pediatric diabetologist. If the value is >6% (nl 4.3-6.4%), the parents are asked to measure several fasting and 1-2 hr post prandial blood sugars at home. If the fasting glycemia is over 120 mg/dl and/or the post-prandial levels are >180 mg/dl on a home glucose monitor, a standard 2 hr oral glucose tolerance test is performed. Families of children persistently positive for more than one autoantibody are provided with keto-diastrix strips and taught how to test urine for presence of glucosuria and ketonuria.

Surveillance of the whole newborn cohort screened at St. Joseph Hospital: The whole cohort is followed for development of IDDM. Further surveillance of the whole cohort is necessary to produce unbiased estimates of the risk of IDDM associated with different HLA genotypes, and predictive value of the genetic markers. At enrollment, parents of all participants authorize release of medical information. Since most of the HLA screened children are members of Kaiser Permanente HMO, hospital, clinic, and pharmacy databases of Kaiser Permanente will be linked yearly with DAISY database, using unique Kaiser ID. The initial linkage of the databases identified Kaiser records for 76% (5981/7849) of the HLA screened children (we are attempting to resolve 107 mismatches for children thought to be Kaiser members). Thus, we can efficiently access, through database linkage, clinical records including ICD codes and insulin prescriptions of at least 76% of the cohort. Membership turnover rate is about 5%/yr. Families of the remaining 24% of the children is contacted yearly by mail, to update the demographic, address and diabetes status information (Surveillance Form). Computerized patient database of the Barbara Davis Center, where over 90% of Denver Metro Area newly diagnosed T1D children are seen, serves as the validation data source for diabetes ascertainment in the whole cohort. Currently, 75 cases of diabetes have been ascertained and 1919 have developed persistent IA, among the initial 37,683 children screened.

This unique cohort is already serving as population laboratory for several additional studies. The celiac disease project (RO1 DK-50979, 9/95-3/2015) allowed us to screen for islet autoantibodies a group of children with the "low risk" HLA-DR3/x genotypes and a group of relatives of patients with celiac disease who are also at an increased risk of T1D. The DR3/x genotype groups represent 15% of T1D cases in the general population. Investigation of Vitamins in Youth (IVY, R01 DK 49654, [name], PI) studies a subset of participants for the associations between vitamin supplements and development of IA and T1D. A supplement to the main study: "Immunizations and type 1 diabetes (DK32493 16S1) investigates the potential link between routine childhood vaccination and IA and T1D. Finally, recently funded Autoimmunity Center of Excellence includes a clinical trial component, where 300 of additional SOC participants will be

screened for the HLA-DR3/4, DQB1\*0302 genotype and those positive, offered participation in a trial of immunological "vaccination" with small amounts of insulin to prevent development of IA and T1D.

HLA typing: The HLA complex, and in particular the DQ and DR loci account for approximately 50% of the familial aggregation of T1D. DAISY is screening all participants for the major T1D susceptibility (HLA-DRB1\*03,\*04 and DQB1\*0302) and protection (DQB1\*0602) alleles. In addition, cases of islet autoimmunity and appropriate controls are fully genotyped for DRB1 and DQB1 subtypes. There are several reasons why we are proposing to continue this subtyping.

First, the PCR-based typing of cord blood is prone to contamination with maternal blood. Eight cases of contamination (0.1%) were inferred from the presence of third allele in the cord blood of the initial 7,537 children screened, however, there may be undetected cases. For instance, if a child is DR1/8 and the mother is DR4/8, and mother's DNA significantly contaminated the cord blood, it would be typed as DR4/x. In the case of homozygosity, e.g., if the child is DR3/3 and the mother is DR3/x their mixed blood would type as DR3/x. Although contamination did not appear to be a significant problem in the screening of cord blood, its exact rate should be determined by retyping the HLA-DR/DQ genotypes on blood samples obtained directly from the child. We propose to accomplish this through subtyping of the DRB1 and DQB1 loci in all children selected for the proposed nested case-control studies using blood sample collected at the 15 months visit. This will also assure the validity of the HLA data used in these studies.

Second, it is unclear whether the associations of different DRB1\*04 subtypes with islet autoimmunity are the same as with T1D. We will determine whether the DRB1\*0403 allele protects from autoimmunity or rather from progression from autoimmunity to diabetes. We also need to subtype the DQB1 alleles of children identified with the usually protective DR2 haplotype. In the Denver population, 34% of children with the DR2/4 DQB1\*0302 genotypes do not have the protective DQB1\*0602 allele on their DR2 haplotypes. Finally, subtyping of the DRB1 and DQB1 alleles may help to understand why more Hispanics (24%) than non-Hispanic whites (17%) have moderate risk HLA genotypes, while the incidence of T1D in Hispanics is only 60% of that in non-Hispanics. On the other hand, among persons with DR4/DR2, more Hispanics than non-Hispanic whites carry a neutral DR2 haplotype, rather than the protective DR2(DRB1\*1501),DQB1\*0602 haplotype and are, in fact, at an increased risk of T1D.

The goal is to collect at least 100 complete families with an IA index child and both parents available (diabetic and non-diabetic siblings will also be asked to participate). DNA will be extracted and aliquotted for these and future studies. We do not request funding for setting up cell lines from these samples given the expense and the amounts of DNA realistically required for the proposed studies. Approximately 20 µg of genomic DNA is obtained from 1 ml of whole blood. With PCR based typing, and at least 10 ml of whole blood per individual, we expect to have sufficient DNA for more than 4,000 PCR based tests per person. If family members are unable to come into the clinic or unwilling to have their blood drawn we will offer to have them collect their DNA using an OROGene DNA self-collection kit.

**Quality control** The procedures included blinded duplicate HLA typing of the same blood sample for all high and moderate risk genotypes and a random 10% of the low risk genotypes (reduced later to 6%). We found only six discordant cases and four occurred in the first ten weeks of the study. None of the 104 samples typed as high risk genotype gave a discordant result on retyping. Repeat typing gave discordant results for 4 out of 519 moderate and 2 of the 354 low risk genotypes. Thus, the reproducibility of the screening was over 99%.Viral studies We will continue to use the method of Pallansch et al. to determine the levels of IgM and IgA antibodies to 17 different enteroviruses (Coxsackie B1-6 and A9, ECHO 4, 6, 9, 11, 30 and 34, enterovirus 71 and poliovirus 1, 2 and 3). The testing will continue to be carried out in the Respiratory and Enteroviral Laboratory at the Centers for Disease Control, Atlanta, GA, under the supervision of [name]. In addition, samples of serum, saliva and rectal swab viral medium were tested for the presence of enteroviral RNA using a well validated assay in the laboratory of [name] in the Department of Pediatrics, University of Colorado, Denver, CO. In addition, appearance of infectious diseases in the previous three months are asked during telephone interviews at ages 3, 6, 9, 12, 15, and 24 months and yearly thereafter.

RNA microarray studies of gene expression: *In collaboration with [name], Director of Diabetes Research and NIDDK Biotechnology Center at the University of Florida, we will initiate RNA microarray studies of gene expression in non-diabetic children with BCA compared to their parents and age, HLA-DR3/4 matched children.*

Identification of other biomarkers: A large nested case-control proteomics study based on the DAISY population has identified seven potential protein/peptide biomarkers of progression to T1D. The biomarkers were cross validated using two approaches: 1) the liquid chromatography-mass spectrometry (LC-MS)-based proteomics analyses approach in collaboration with colleagues from the Pacific Northwestern National Laboratory (PNNL); and 2) the aptamer approach (Somalogic, Boulder, CO). Additional protein biomarkers have been reported from the DIPP, nPOD and other studies. We are proposing to apply the newest version of the SOMAscan™ assay that can measure up to 3,000 proteins simultaneously across a wide range of concentrations. This SOMA scan assay is available through the Genomics and Microarray Core Laboratory at the University of Colorado and can be customized to capture all targets pertinent to this proposal. Additionally, we have utilized this same case-control cohort to identify metabolomics signatures characteristic of islet autoimmunity and progression to T1D. In collaboration with Metabolon, the analysis of serial plasma samples may identify up to 2,200 named metabolites. The study is powered to confirm previously identified associations as well as identify potential new metabolic pathways involved in the development of IA and T1D. Finally, longitudinal changes in the metabolic profiles identified in the study participants will be related to detailed dietary records, infections, and other environmental stressors, e.g., antibiotic use, during the follow-up period leading to diabetes.

T-cell study: T-cell reactivity to autoantigens will be studied in autoantibody positive siblings and negative control children with HLA DR3/4 DQB1\*0302 as well as non-diabetic parents of these children. This work will utilize a standard proliferation assay system using unfractionated peripheral blood mononuclear cells.

Infant diet Under the current DAISY protocol, infant diet data is collected prospectively via periodic telephone interviews conducted by a professional interviewer at 3, 6, 9, 12 and 15 months. Minor modifications to this protocol are proposed for the additional general population newborns to be enrolled. The questionnaire (UPDATE3\_15) is included. The infant diet portion of this questionnaire is a modification of a questionnaire that was found to have relatively good agreement with pediatric records. During each interview, parents will be asked to detail their infant's diet over the past 3 months (i.e. during a 6-month interview, the mother would be asked to recall the infant diet in the 3rd, 4th and 5th months). The interviewer records the date a milk/food on the list was introduced into the diet. For infant formulas, the type, including brand name is recorded. The types of cereal (e.g. rice, oatmeal) and fresh milks (e.g. cow, goat) are also recorded separately. Then the frequency of consumption of that food is averaged over a month and is recorded as number of servings per day. For breast-milk, this would be number of feedings per day; for formulas and milks, it would be recorded as the number of baby bottles per day and for solid food, it would be number of discrete servings per day, without distinguishing serving size. If the milk/food was introduced mid-month, the frequency of consumption is recorded as the average from the start-date to the end of the month. In addition, frequencies of consumption are recorded separately for juice, fruit, vegetables, meat, breads, dairy products, eggs, sweets and snacks. Vitamin supplementation during infancy, including brand name and dose, will also be collected.

Early childhood diet will be measured annually using the Willett FFQ that has been altered for use in pre-school children. The Willett FFQ has been found to be reliable in children while using parental recall. All mothers of children will be given a food frequency questionnaire asking them to record their child's diet in the previous year. As part of the FFQ, extensive information is collected on vitamin supplementation. This food frequency questionnaire will be first administered when the participating child is 2 years old and repeated annually. In addition, two 24-hr recalls per

year will be administered to the participants. The diet recall forms are included. The diet recall will be used to calibrate the FFQ for each participant. From the age of 10 years on, we ask the children to complete the Youth/Adolescent Questionnaire (YAQ), which is a modification of the Willett FFQ that is meant to be filled out by the child alone.

Dietary antigen exposure: All FFQ forms will be sent to the Channing Laboratory for data entry and analysis. All training, data entry and analyses for the 24 hr recall will be performed by the Energy Balance Laboratory of the Center for Human Nutrition ([name], Director) at the University of Colorado. Nutrient profiles for both methods will be produced as a result of this analysis. Some of the variables of interest for the proposed study include total protein intake (i.e. grams per day), dairy protein intake, vegetable protein intake and nitrate/nitrite intake. Vitamin intake (i.e. antioxidants) will also be of interest as a potential effect modifier or protective factor. Total vitamin intake will be calculated from the vitamin supplementation data and vitamin content of consumed foods. The infant diet exposures will be calculated based on the infant diet food frequency (contained in UPDATE3\_15). In order to calculate exposure quantities, an average serving size across subjects is assumed. Based on the frequency of servings, exposures to specific dietary proteins, i.e. dairy, animal, vegetable, wheat, etc., will be calculated on a monthly basis. In order to do this, we will use the Minnesota Nutrition Data System (NDS) to assign average nutrient quantities (i.e. grams of protein per day, etc) to the milks and foods in each category listed in the infant food frequency questionnaire. Additional measurements of dietary and viral exposures are described under Specific Aim 2.

Immunizations: Immunization records will be obtained, participants will be asked to sign a separate authorization form which will allow us to gather this information.

